15.2 Clinical Global Impression of Severity (CGI-S) and Change (CGI-C)

The CGI-S scale will be used to record the severity of illness (sialorrhea) on Day 1 (i.e., study baseline) before the first injection of study drug, at each subsequent study visit or, if applicable, at discontinuation from the study. CGI-S will be assessed by a trained assessor on a 7-point scale ranging from “normal” to “among the most extremely ill patients” (Appendix C). The CGI-C, used to record change or improvement in illness from baseline (i.e., pre-injection) of each treatment session, will be assessed at each study visit after Day 1 by the assessor on a 7-point scale ranging from “very much improved” to “very much worse” (Appendix C). Both CGI scales will be completed independent of the subject’s self-assessment (PGI-S and PGI-C) so neither party knows how the other has rated the scales.

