Abbreviations: AE = adverse event, BP = blood pressure, C-SSRS = Columbia Suicide Severity Rating Scale, DFSS = Drooling Frequency and Severity Scale, HIPAA = Health Insurance Portability and Accountability Act, RR = respiration rate, Temp = temperature, USFR = unstimulated salivary flow rate, VAS = visual analog scale, wks = weeks

- (a) All screening and baseline assessments and results must be available before injection of MYOBLOC.
- (b) Telephone follow-up.
- (c) Office visit.
- (d) Office visit. Serves as last visit of current treatment session and first visit of subsequent treatment session. Study drug injection will occur after the 13-week assessments have been completed for the prior treatment session.
- (e) Must be obtained before conducting any study procedure.
- (f) Includes baseline history of aspiration, aspiration pneumonia, choking, and dysphagia.
- (g) Includes 4 bite-wing radiographs or panoramic imaging (if edentulous or if bite-wing x-rays are difficult due to limited teeth). If the subject has no teeth, then the dentist will determine if panoramic imaging is required at any visit after screening.
- (h) Females of childbearing potential only.
- (i) Forced vital capacity will be measured in all subjects with amyotrophic lateral sclerosis and in other subjects if warranted at the discretion of the Investigator.
- (j) When possible, assessments should be done by the same person in a given subject to ensure consistency throughout the study.
- (k) Global measure of effectiveness must be completed before USFR.
- (l) Subject-rated via entry in diary (not during study visit), daily for first 2 weeks after study drug injection and then weekly for remainder of treatment session.
- (m) Subjects will receive injections guided by external anatomical landmarks or by external anatomical landmarks with ultrasound-guided confirmation. Sites designated as "ultrasound" sites will perform all their injections with ultrasound-guidance.
- (n) Subjects will be injected after completion of all assessments and then will be contacted by telephone 24 hours (± 1 day) post-injection to inquire about their health status and remind the subject to complete their diary.
- (o) Telephone follow-up by the study staff will be conducted 1 week (± 1 day) after study drug injection to assess how the subject feels, document adverse events as appropriate, document any new medications the subject may be taking, and remind the subject to complete their diary.

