2.6.1 Effectiveness measures

Several effectiveness measures are assessed over each of the treatment Sessions 1 through 4 at the injection visit (i.e., Day 1, and Weeks 13, 26, and 39), 4 weeks post-injection (i.e., Weeks 4, 17, 30, and 43), 8 weeks post-injection (i.e., Week 8, first treatment session only), and 13 weeks post-injection (i.e., Weeks 13, 26, 39, and 52). Where applicable, the measurement value obtained at pre-injection of each treatment session (i.e., Day 1 and Weeks 13, 26, and 39 for each of the 4 treatment sessions, respectively) is defined as the baseline of the corresponding measures. For the CGI-C and PGI-C, the corresponding severity score observed at pre-injection of each treatment session will be used as the baseline measurement of the corresponding session in analysis.

Unstimulated Salivary Flow Rate (USFR)

The USFR (g/minute) is the salivary flow rate assessed by the independent assessor in an unstimulated state (i.e., at least 1 hour postprandial) at screening, just before the first injection of study drug (Day 1) to establish a baseline salivary flow rate, and at each subsequent study visit (Appendix B of the protocol). To determine USFR at each study

visit, saliva will be collected over a 5-minute collection period using weighing cups

hey will be asked to expectorate, as needed, any saliva that accumulates in their mouth into the pre-weighed cup during the 5-minute collection period.

Although not a rating scale, the same person should conduct this assessment throughout the study to minimize collection technique bias.

Clinical Global Impression of Severity (CGI-S) and Change (CGI-C)

The CGI-S scale is used to record the severity of illness (sialorrhea) on Day 1 (i.e., study baseline) before the first injection of study drug, at each subsequent study visit or, if applicable, at discontinuation from the study. CGI-S will be assessed by a trained assessor on a 7-point scale ranging from “normal” to “among the most extremely ill patients” (Appendix C of the protocol). The CGI-C, used to record change or improvement in illness from baseline (i.e., pre-injection) of each treatment session, will be assessed at each study visit after Day 1 by the assessor on a 7-point scale ranging from “very much improved” to “very much worse” (Appendix C of the protocol). Both CGI scales will be completed independent of the subject’s self-assessment (PGI-S and PGI-C) so neither party knows how the other has rated the scales.

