2.9.1 Effectiveness analysis

As subjects receive multiple single-dose injections, each single-dose injection plus its follow-up period will be considered as a treatment session.

Effectiveness measures obtained over each of the treatment sessions include USFR, CGI-S, CGI-C, DFSS-I, DFSS-S, PGI-S, PGI-C, and DIS at the injection visit (i.e., Day 1, except for CGI-C and PGI-C, and Weeks 13, 26, and 39), 4 weeks post-injection (i.e., Weeks 4, 17, 30, and 43), 8 weeks post-injection (i.e., Week 8, first treatment session only), and 13 weeks post-injection (i.e., Weeks 13, 26, 39, and 52). The injection visit of Day 1 and Weeks 13, 26, and 39 is considered the baseline (or pre-injection), respectively, for each of the consecutive treatment sessions 1 through 4.

For each treatment session, effectiveness analysis of the treatment response will be performed on USFR change from pre-injection, DFSS-I change from pre-injection, and DFSS-S change from pre-injection, CGI-S, CGI-C, PGI-S, PGI-C, and DIS change from pre-injection, at each of the post-injection time points using a t-test.

In addition, the proportion of treatment responders will be reported for the CGI-C and PGI-C at both pre-injection and post-injection time points over each treatment session. Before the analysis, the CGI-C and PGI-C will be dichotomized into 2 categories, with "very much improved" and "much improved" into 1 category and the remaining levels in the other category.

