4.4 Efficacy Results and Tabulations

Descriptive and inferential statistics of USFR (g/minute) and changes from pre-injection at Day 1 to Weeks 4, 8 and 13, for Treatment Session 1 and from each subsequent pre-injection at Weeks 13, 26 and 39 (Treatment Session 2, 3 and 4) to 4 and 13 weeks following it respectively, will be presented for the ITT population.

Descriptive and inferential statistics of DFSS-I and changes from pre-injection at Day 1 to Weeks 4, 8, and 13, for Treatment Session 1 and from each subsequent pre-injection at Weeks 13, 26 and 39 (Treatment Session 2, 3 and 4) to 4 and 13 weeks following it, respectively, will be presented for the ITT population.

Descriptive and inferential statistics of DFSS-S and changes from pre-injection at Day 1 to Weeks 4, 8, and 13, for Treatment Session 1 and from each subsequent pre-injection at Weeks 13, 26 and 39 (Treatment Session 2, 3 and 4) to 4 and 13 weeks following it, respectively, will be presented for the ITT population.

Descriptive and inferential statistics of CGI-S and changes from pre-injection at Day 1 to Weeks 4, 8, and 13, for Treatment Session 1 and from each subsequent pre-injection at Weeks 13, 26 and 39 (Treatment Session 2, 3 and 4) to 4 and 13 weeks following it, respectively, will be presented for the ITT population.

Descriptive and inferential statistics of CGI-C at pre-injection (except for Day 1), and at Weeks 4, 8, and 13 for Treatment Session 1 and from each subsequent pre-injection at Weeks 13, 26 and 39 (Treatment Session 2, 3 and 4) to 4 and 13 weeks following it, respectively, will be presented for the ITT population.

Descriptive and inferential statistics of the proportion of the CGI-C treatment responders with much improved or better at pre-injection (except for Day 1) and at Week 4, 8, 13 weeks post injection for Treatment Session 1 and from each subsequent pre-injection at Weeks 13, 26 and 39 (Treatment Session 2, 3 and 4) to 4 and 13 weeks following it, respectively, will be presented for the ITT population.

Descriptive and inferential statistics of PGI-S and changes from pre-injection at Day 1 to Weeks 4, 8, and 13, for Treatment Session 1 and from each subsequent pre-injection at Weeks 13, 26 and 39 (Treatment Session 2, 3 and 4) to 4 and 13 weeks following it, respectively, will be presented for the ITT population.

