Descriptive and inferential statistics of PGI-C at pre-injection (except for Day 1), and at Weeks 4, 8, and 13 for Treatment Session 1 and from each subsequent pre-injection at Weeks 13, 26 and 39 (Treatment Session 2, 3 and 4) to 4 and 13 weeks following it, respectively, will be presented for the ITT population.

Descriptive and inferential statistics of the proportion of the PGI-C treatment responders with much improved or better at pre-injection (except for Day 1) and at Week 4, 8, 13 weeks post injection for Treatment Session 1 and from each subsequent pre-injection at Weeks 13, 26 and 39 (Treatment Session 2, 3 and 4) to 4 and 13 weeks following it, respectively, will be presented for the ITT population.

Descriptive and inferential statistics of DIS and changes from pre-injection at Day 1 to Weeks 4, 8, and 13 for Treatment Session 1 and from each subsequent pre-injection at Weeks 13, 26 and 39 (Treatment Session 2, 3 and 4) to 4 and 13 weeks following it, respectively, will be presented for the ITT population.

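### In Sessions 2–4 the pre-injection CGI-C responder proportion is the previous injection's 13-week result, so a pre- to post-injection contrast on it does not test the current injection (likewise PGI-C, if rated against the most recent injection)

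*SAP*

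**What the plan says.** **Analysis.** SAP 2.9.1 states that "the proportion of treatment responders will be reported for the CGI-C and PGI-C at both pre-injection and post-injection time points over each treatment session". Protocol 17.9 has nearly the same sentence. SAP 4.4 then plans "Descriptive and inferential statistics of the proportion of the CGI-C treatment responders with much improved or better at pre-injection (except for Day 1", running from the pre-injection visits of Sessions 2–4 to the visits 4 and 13 weeks later. It repeats this for the patient rating: "Descriptive and inferential statistics of the proportion of the PGI-C treatment responders with much improved or better at pre-injection (except for Day 1". No test is named for the proportion. A responder is a subject in one of the two best change categories.

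**Timing.** SAP 2.9.1 says "The injection visit of Day 1 and Weeks 13, 26, and 39 is considered the baseline (or pre-injection), respectively", for Sessions 1 to 4. The same section gives the late outcome visits as "13 weeks post-injection (i.e., Weeks 13, 26, 39, and 52". Weeks 13, 26 and 39 are in both lists. The schedule note in SAP 2.3 confirms that this is one visit: "Serves as last visit of current treatment session and first visit of subsequent treatment session".

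**Reference state.** Under Protocol 15.2, CGI-C records "change or improvement in illness from baseline (i.e., pre-injection) of each treatment session", and SAP 2.6.1 agrees. PGI-C is looser. Protocol 15.3 and SAP 2.6.1 let it refer either to Day 1 or to the state just before the latest injection.

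**The concern.** A change rating already contains its own comparison. Rated against its own session's starting point, every subject is unchanged at the moment of injection, so the pre-injection responder proportion is 0% by definition. The number that the plan puts in that place for Sessions 2–4 was rated against an earlier starting point and belongs to an earlier injection.

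A reader of the Session 2 table would take a pre- to post-injection comparison as evidence on the second injection. In fact a subject who is still much improved at Week 13 and keeps that benefit should be rated about unchanged at Week 17, and would be counted as a lost responder. The response tables for repeat injections serve the secondary objective, the magnitude of therapeutic response over up to a year. An apparent loss of response there could be an artefact of the reference state.

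**Working it through.** **1. What each CGI-C rating measures**

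| Visit | Rated against | Describes | Place in the tables |
|---|---|---|---|
| Week 13 | Day 1 | Injection 1 at 13 weeks | Session 1, 13 weeks; Session 2, pre-injection |
| Week 17 | Week 13 | Injection 2 at 4 weeks | Session 2, 4 weeks |
| Week 26 | Week 13 | Injection 2 at 13 weeks | Session 2, 13 weeks; Session 3, pre-injection |

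The null hypothesis of a pre/post contrast in Session k is therefore that the responder probability 13 weeks after injection k−1 equals that at 4 (or 13) weeks after injection k, each on its own reference. It is not that injection k has no effect.

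**2. Direction of the error.** Let every injection work equally well, with improvement over Day 1 of D4 at 4 weeks and D13 at 13 weeks. The ratings are then:

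- Session 2 pre-injection (Week 13): D13
- Week 17: D4 − D13
- Week 26: D13 − D13 = 0

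The Week 17 contrast is (D4 − D13) − D13 = D4 − 2·D13, which is negative once more than half the peak benefit remains. The Week 26 contrast is 0 − D13, negative for any remaining benefit. In Sessions 3 and 4 the pre-injection rating is itself 0, so the fall belongs mainly to Session 2.

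**3. Size.** There is no plan figure to reproduce: SAP 2.5 gives N = 187 without an estimation, and neither document gives responder rates or residual benefit. The following are assumptions: peak improvement with mean 2.5 and SD 1.0 units, rating noise SD 0.5, responder at 2 units or more, a fraction r of the peak left at 13 weeks, and an exact McNemar test at two-sided 0.05. If a rating captures a fraction f of the peak, the responder share is close to

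Φ((2.5f − 2) / √(f² + 0.25)),

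with f = 1 at Week 4, r at Week 13, 1 − r at Week 17 and 0 at Week 26. For r = 0.6:

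- Week 13: (1.5 − 2)/√0.61 = −0.64, giving 26%
- Week 17: (1.0 − 2)/√0.41 = −1.56, giving 6%
- Week 26: −2/0.5 = −4, giving 0%

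Simulation (N = 187, 400 runs) agrees with these:

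| Peak benefit left (r) | Labelled pre-injection | Week 17 | Week 26 | Runs with significant fall, Week 17 | Same, Week 26 |
|---|---|---|---|---|---|
| 0% | 0% | 67% | 0% | 0% | 0% |
| 25% | 0.7% | 44% | 0% | 0% | 0% |
| 50% | 14.6% | 14.6% | 0% | 2% | 100% |
| 60% | 26% | 6% | 0% | 100% | 100% |
| 75% | 45% | 0.7% | 0% | 100% | 100% |

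At r = 50% the same drug effect shows no difference in Session 2 (14.6% against 14.6%) but a significant rise in every run in Session 3 (0% against 14.4%). With Day 1 as the common reference, Week 17 is about 67% at every r, with a significant rise in all runs, and a significant Week 26 fall occurs in at most 3% of runs. The change of reference produces the fall.

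**4. A second illustration: injection k adds nothing.** Assume 5% are rated responders spontaneously, independent ratings, n = 150 and an exact McNemar test. With 5%, 10%, 15%, 20% and 30% still responders at re-injection, the contrast rejects in about 3%, 30%, 79%, 98% and 100% of runs. From 10% upward every rejection is towards fewer responders. If instead 50% respond at 4 weeks, power is 100%, 93%, 37% and 11% at residual rates of 20%, 30%, 40% and 45%. These power figures are rough: they hold the later rate at 50% whatever the residual, whereas step 2 shows that residual benefit lowers it.

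**The case against.** **The test is not spelled out.** SAP 2.9.1 says only that the proportion is reported. SAP 4.4 names no method, and confidence intervals alone would count as inferential. For USFR, DFSS, DIS and the severity scales, 4.4 speaks of changes from pre-injection; the CGI-C, PGI-C and responder paragraphs omit this. This stands in part. A reader might infer that the SAP prescribes a paired test with the error rates above; it does not. But the responder paragraphs still run from each later pre-injection visit to 4 and 13 weeks, and the pre/post contrast is their natural reading.

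**SAP 2.6.1 names a different baseline.** It makes the pre-injection severity score the baseline for CGI-C and PGI-C. A severity score cannot be the baseline of a proportion rated much improved. Excluding Day 1 also shows that the change rating is meant, because severity is recorded on Day 1 and change is not.

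**Re-injection follows return to baseline.** If that holds, the labelled pre-injection proportion is near zero and the contrast shows a rise, as in the first two table rows. This stands as a limit on size. Return is judged by the investigator, and Protocol 10 also sets a latest time of 15 weeks, so residual benefit is possible, but no document says how common it is.

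**PGI-C may be anchored to Day 1.** If it were throughout, the ratings would share one reference and the false fall would not arise, though the pre-injection value would still be the earlier 13-week rating.

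**Removing the column does not stop the scale resetting.** True: with 25% of peak benefit left, Week 17 still shows 44% against 67% at Week 4, although both injections work equally. Hence the footnote and the severity comparison in the fix.

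**Conclusion.** The concern holds for CGI-C on the documents' own definitions of visit and reference state. It holds for PGI-C only if the reference is the most recent injection. Any pre- to post-injection inference on these ratings in Sessions 2–4 compares two injections on two reference states.

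The size is conditional. It is negligible if subjects have returned to baseline. If benefit persists, the contrast can lose power or show a false fall, mainly in Session 2; at the 4-week visit a fall needs more than half the peak benefit to remain in the model used. All percentages rest on assumed response and residual rates and an assumed McNemar test.

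A reader might infer that all three later sessions will show a false fall, or that the effectiveness results as a whole are unsound. Neither is supported. Changes in USFR, DFSS, DIS, CGI-S and PGI-S do not have this change-rating problem, and the primary objective is safety. The point affects how the CGI-C and PGI-C tables are read, and is worth correcting for that reason.

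**What to change.** In SAP 2.9.1 and 4.4:

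- Remove the pre-injection CGI-C and PGI-C values and responder proportions from Sessions 2–4, and make no pre- to post-injection inference on them.
- Report the Week 13, 26 and 39 ratings once, as the 13-week outcome of the session in which they were rated.
- Give responder n/N with an exact (Clopper-Pearson) 95% CI at each post-injection time point.
- State one reference for PGI-C, consistent with Protocol 15.3 and SAP 2.6.1.
- Footnote that the CGI-C reference resets at each injection, so responder rates are not directly comparable between sessions when benefit persists. For comparison across sessions, use CGI-S and PGI-S change from Day 1.

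The cost is SAP wording, one column fewer in the change-rating tables, and a severity summary from data already collected. What is lost is a comparison that does not address the current injection. The change also removes a clash in SAP 2.8, which would impute a missing Week 13 rating by the site average in its pre-injection role but not in its post-injection role, with no rule for turning an average into a responder status.

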2.9.2 Safety analysis

Safety measures include adverse events, adverse events of special interest (AESI), dental adverse events (DAE), adverse events associated with distant spread of toxin effect, vital signs and weight, physical exam, neurological exam, dental exam, oral exam, and clinical laboratory tests, as well as lung functioning test for ALS subjects. Adverse events will be coded using the Medical Dictionary for Regulatory Activities (MedDRA) adverse event dictionary.

Like for effectiveness analyses, the baseline for safety analysis includes the pre-injection visits of Day 1, and Weeks 13, 26, and 39, respectively, for each of the treatment sessions 1 through 4.

Drug Exposure

Frequency of drug exposure will be calculated based on the number of injections of study drug administered. Duration of drug exposure will be calculated for each subject for the average duration of individual treatment sessions and total duration of treatment sessions, with the former being the average of the durations of individual treatment sessions the subject has received and the latter being the sum of the durations of individual treatment sessions the subject has received. Duration of drug exposure will be summarized for the safety population as defined in Section 3.1.

Early Termination

Subjects' study disposition will be summarized. A listing will be provided for all early terminations. This listing will include a subject's demographic variables, primary diagnosis, number of injections administered, and the primary reason for early termination.

Adverse Events, AESI, and DAE

All of adverse events will be coded for preferred terminologies using MedDRA. An AE that occurs on the 1st injection date or later will be defined as a TEAE. An AE with start date missing and no valid stop date or stop date being after the first injection date will be considered as a TEAE. TEAEs will be further separated by treatment session.

TEAEs, AESIs, DAEs, and adverse events associated with distant spread of toxin effect will be analyzed by session. Frequency of these types of adverse events will be calculated for each body system (or system organ class, SOC), by preferred term, for number of subjects and proportion reporting the event. The severity of adverse events and the relationship to study medication will be summarized for each body system and preferred term.

Withdrawals due to adverse events will be summarized for each body system and preferred term. Serious adverse events (SAEs) (including deaths) will be listed for individual events.

Narratives will be provided for all deaths, non-fatal serious adverse events, and subjects withdrawn due to adverse events.

Vital Signs and Weight

Vital signs and weight will be summarized descriptively by treatment session at pre-injection (i.e., Day 1 and Weeks 13, 26, and 39) and at each post-injection time point of 4 weeks post-injection (i.e., Weeks 4, 17, 30, and 43), 8 weeks post-injection (i.e., Week 8 first treatment session only), and 13 weeks post-injection (i.e., Weeks 13, 26, 39, and 52). The change scores in vital signs and weight from baseline at 4 weeks, 8 weeks (first treatment session only), and 13 weeks post-injection will be summarized descriptively.

Neurologic Exam

Abnormal findings of neurological exam data will be listed, respectively, for individual subjects.

Lung Functioning Test

Findings of forced vital capacity (FVC) data will be listed, respectively, for individual subjects.

Physical Examination

A complete Physical Examination was performed at Screening, Week 4, Week 13, Week 26, Week 39, Week 52, and Early Discontinuation. A brief Physical Examination was performed at Day 1, Week 8, Week 17, Week 30, and Week 43 when body weight, height and body mass index (BMI) were recorded. If any of the Physical Examination findings were abnormal and clinically significant prior to treatment, the event was recorded as medical history, while if occurred after treatment the event was recorded as a TEAE.

Suicidality Assessment

For each treatment session, each of the three C-SSRS subscales (suicidal ideation, suicidal behavior, and intensity of suicidal ideation) will be summarized descriptively for continuous variable at each pre-injection visit (i.e., Day 1 and Weeks 13, 26, and 39) and at each post-injection time point of 4 weeks post-injection (i.e., Weeks 4, 17, 30, and 43), 8 weeks post-injection (i.e., Week 8, first treatment session only), and 13 weeks post-injection (i.e., Weeks 13, 26, 39, and 52). The change scores in C-SSRS subscales from pre-injection at 4 weeks, 8 weeks (first treatment session only), and 13 weeks post-injection will be summarized descriptively.

Dental Examination and Oral Examination

Abnormal findings of dental exam and oral exam will be listed, respectively, for individual subjects. Dental adverse events will be included in the analysis of adverse events.

Laboratory Assessments

For each treatment session, clinical laboratory tests of hematology, chemistry, and urinalysis (specific gravity and pH) will be summarized descriptively at available visits. Qualitative analysis of laboratory tests in terms of abnormality will be performed, using the shift-table method, for individual post-screening visits. Abnormal findings of clinical laboratory tests for individual subjects will be provided by data listing.

Pregnancy Test

Any positive findings of the pregnancy test will be listed for individual subjects.

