17.6 Safety Endpoints

Safety endpoints include adverse events and AESI, vital signs and weight, neurological exam, physical examination, dental exam, C-SSRS, and clinical laboratory tests. Adverse events will be coded using the Medical Dictionary for Regulatory Activities (MedDRA) adverse event dictionary.

For safety endpoints, records with valid data within each visit or assessment time point will be identified for initial and repeat, where applicable. The initial record will be used in statistical analysis, whereas all records will be presented in data listings. Missing or invalid data will be treated as missing for the corresponding visit or time point.

The baseline of each treatment session consists of the corresponding measurement value obtained at pre-injection of each treatment session (i.e., Day 1, Weeks 13, 26, and 39).

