17.9 Statistical Methods for Effectiveness

As subjects will receive multiple single-dose injections, each single-dose injection plus its follow-up period will be considered as a treatment session. Post-injection effectiveness endpoints over each of the treatment sessions include USFR, CGI-C, CGI-S, DFSS-I, PGI-C, PGI-S, DIS, and DFSS-S at the injection visit (i.e., Day 1, Weeks 13, 26, and 39), 4 weeks post-injection (i.e., Weeks 4, 17, 30, and 43), 8 weeks post-injection (i.e., Week 8, first Treatment Session only), and 13 weeks post-injection (i.e., Weeks 13, 26, 39, and 52). The pre-injection time points are Day 1 and Weeks 13, 26, and 39 for each of the consecutive treatment sessions. Missing post-injection measurements will not be imputed, whereas missing measurements at the pre-injection of each treatment session will be imputed by the site-specific average of those subjects who receive the treatment at the corresponding treatment session.

For each treatment session, effectiveness analysis of the treatment response will be performed on USFR change from pre-injection, CGI-C, CGI-S, PGI-C, PGI-S, and DIS change from pre-injection, DFSS-I change from pre-injection, and DFSS-S change from

pre-injection at each of the post-injection time points for the ITT population, using a paired t-test. The ITT population will be grouped into three groups by the actual doses the subject received at each session as the following: low dose (2,500 to 2,999 Units), medium dose (3,000 to 3,499 Units), and high dose (3,500 Units).

In addition, the proportion of treatment responders will be reported for the CGI-C and PGI-C at both pre-injection and post-injection time points over each treatment session. Before the analysis, the CGI-C and PGI-C variables will be dichotomized into 2 categories, with “very much improved” and “much improved” into 1 category and the remaining levels in the other category.

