1 INTRODUCTION

1.1 Trial Objectives

The primary objective of this study is:

- To determine the long-term safety and tolerability of MYOBLOC® (administered intraglandularly as a single total dose of 3,500 Units) treatments every 13 weeks over a maximum possible duration of 1 year in adult subjects with troublesome sialorrhea.

The secondary objective of this study is:

- To assess the magnitude of therapeutic response of MYOBLOC (administered intraglandularly as a single total dose of 3,500 Units) using effectiveness assessments performed at intervals after treatments every 13 weeks over a maximum possible duration of 1 year.

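### Change is re-based at every injection, so the SAP text gives no within-subject change from Day 1 after Week 13 to describe the 1-year course

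*SAP*

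**What the plan says.** The re-basing comes from the protocol. Section 17.6 says: "The baseline of each treatment session consists of the corresponding measurement value obtained at pre-injection of each treatment session". Section 17.9 says for effectiveness: "The pre-injection time points are Day 1 and Weeks 13, 26, and 39 for each of the consecutive treatment sessions".

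The SAP follows. Section 2.9.2 on safety reads: "Like for effectiveness analyses, the baseline for safety analysis includes the pre-injection visits of Day 1, and Weeks 13, 26, and 39". Under vital signs and weight it summarizes "The change scores in vital signs and weight from baseline at 4 weeks, 8 weeks (first treatment session only), and 13 weeks post-injection", by session. For the effectiveness measures, section 4.4 takes change from Day 1 in Session 1 and after that "from each subsequent pre-injection at Weeks 13, 26 and 39 (Treatment Session 2, 3 and 4) to 4 and 13 weeks following it". C-SSRS change is handled in the same way.

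Both objectives in SAP 1.1 concern "treatments every 13 weeks over a maximum possible duration of 1 year".

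Three further rules bear on the point:
- **Re-injection** (protocol 10 and 13.2, SAP 2.9): it waits until the Investigator judges that the subject is back at baseline. Protocol 10 sets limits of 11 and 15 weeks from the prior injection.
- **Missing values** (SAP 2.8, protocol 17.9): post-injection effectiveness values are not imputed, but a missing pre-injection value is replaced by the average at that site for the session.
- **Neurologic exam**: protocol 17.7 plans a paired change in the average score from Day 1 to Weeks 13 and 52. SAP 2.9.2 and 5.8 only list abnormal findings.

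**The concern.** Per-session change answers one question: what did this injection do? It does not say where a subject stands after several injections compared with the start of the study, which is a natural question for a study with a 1-year objective. A slow drift, for instance in weight, would be split across up to four re-based changes. The return-to-baseline rule concerns sialorrhea, so it does nothing to hold weight or vital signs near their Day 1 values.

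The protocol itself appears to use a Day 1 comparison after later injections. Section 12.3 describes loss of effectiveness at the 4-week visit of subsequent injections against the score at baseline (Day 1). This could mean Day 1 of the session, but the same phrase is used there for the initial treatment. The SAP text tabulates no USFR change on that scale after Week 13.

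The imputation rule raises a smaller, separate question: a paired analysis may contain a baseline that the subject never produced.

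**Working it through.** The plan states no figure on this point, so there is none to reproduce.

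**1. Visits covered.** The office visits after Day 1 (SAP 2.2 and 2.6.2) and the reference for change (SAP 2.9.1, 2.9.2 and 4.4) are:

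| Visit | Reference for change |
|---|---|
| Weeks 4, 8, 13 | Day 1 |
| Weeks 17, 26 | Week 13 |
| Weeks 30, 39 | Week 26 |
| Weeks 43, 52 | Week 39 |
| Early discontinuation | no change analysis named |

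There are 9 visits. Three have a change from Day 1 and 9 - 3 = 6 have none.

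**2. Can the 1-year change be rebuilt from the planned tables?** Write Y1 for the Day 1 value and Yk for the value at Week k. Then

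Y52 - Y1 = (Y13 - Y1) + (Y26 - Y13) + (Y39 - Y26) + (Y52 - Y39).

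If the same subjects contribute throughout and nothing is imputed, the four session means add up to the 1-year mean. The SD does not follow. The variance of the sum also needs the covariances between the four changes, which are not reported. As an illustration, assume one SD s at every visit and one correlation r between any two visits. Each session change then has SD s x sqrt(2(1 - r)), and so does Y52 - Y1. Adding the four as if independent gives sqrt(4) = 2 times that SD, whatever r is.

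**3. Different subjects at different visits.** Sessions 3 and 4 are marked optional (protocol Table 2). Planned participation may be 26 weeks (protocol 10). ALS subjects need be available for only 6 months (protocol 11.1.1). Subjects may be withdrawn for lack or loss of effectiveness (protocol 12.3). Means at Day 1 and Week 52 may thus describe different groups, and the sum of session means need not equal the change in any one group.

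A simulation shows the pattern. All its inputs are assumed, so it says nothing about size in this trial. Between-subject variance is 0.8 and residual variance 0.2. The mean slope is -0.1 SD per session (SD of slopes 0.1). Loss after each of the first three sessions is about 10% at the mean slope and higher with steeper decline, leaving 69% at the end.
- All subjects, Day 1 to Week 52: -0.402 SD
- Sum of session means: 0.101 + 0.090 + 0.086 + 0.075 = 0.352, so -0.352 SD
- Paired change in those remaining: -0.306 SD

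**4. Imputation.** Suppose Week 13 is missing for a subject who is injected. As the Session 1 outcome, Y13 - Y1 stays missing. As the Session 2 baseline, Y13 becomes the site mean m, so the Week 17 change is

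Y17 - m = (Y17 - Y13) + (Y13 - m).

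The last term is the subject's unobserved distance from the site mean. In a true pair it would not be there. Notes (a) and (d) to the schedule tables place the assessments before each injection, so such cases should be few. The documents give no count.

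**5. What is unaffected.** TEAEs count from the first injection (SAP 2.9.2). Laboratory tests keep a screening reference through End of Study (SAP 5.11).

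**The case against.** The strongest reply is that nothing here is wrong. The per-session baseline is prespecified in the protocol and the SAP applies it. The secondary objective asks about response at intervals after treatments, which is a per-injection question. One year is a maximum, and the later sessions are optional. Values at Day 1 and every later visit are summarized anyway. PGI-C may even be rated against Day 1, since protocol 15.3 allows either Day 1 or the most recent injection as reference. All of this stands, and it limits the point to a missing supplementary description.

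Two further objections also stand. First, a paired Week 52 change covers only subjects still in the study. In the simulation above it lay further from the all-subject value than the sum of session means did. The added columns must therefore show n and say whom they describe. Second, the SAP was written with some knowledge of the data: section 3.4 reports that the two populations differ by one subject, and section 2.9 that most subjects received 3,500 Units. Additions at that stage belong under a supplementary label, without tests.

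A reader might also take the plan to report "the proportion of treatment responders will be reported for the CGI-C and PGI-C at both pre-injection and post-injection time points" as evidence that subjects do not return to baseline before re-injection. It is not: a planned table is no result. It shows only that the plan leaves the question open.

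**Conclusion.** The gap is real but modest. For effectiveness measures, vital signs, weight and C-SSRS, the SAP text specifies no within-subject change from Day 1 at 6 of the 9 later office visits or at early discontinuation. The mean 1-year change could be derived if data were complete; its SD and confidence interval could not.

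Stronger readings are tempting but not supported. Re-basing is not a departure from the protocol for these measures, and it does not invalidate the per-session analysis. It does not hide adverse events or laboratory changes. Nor can one say that the planned tables lack the comparison: the shells listed in SAP sections 7 to 9 are not in the text available, which keeps confidence at medium. No effect size can be given, because residual effect at re-injection, attrition and within-subject correlation are not in the documents.

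The imputation rule is a separate weakness that should rarely apply. The neurologic score is the one place where the protocol did plan a paired change from Day 1 to Week 52 and the SAP text does not carry it over. Overall this is an improvement to consider.

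**What to change.** 1. In SAP 2.9.1, 2.9.2, 4.4 and 5.7, keep the per-session change. Beside it, add supplementary descriptive change from the observed Day 1 value (n, mean, SD, 95% CI, no test) at each later office visit and at early discontinuation, for weight, vital signs, USFR, CGI-S and PGI-S. State that Week 52 covers only subjects still in the study.
2. Add no such column for DFSS-S (the first real diary entry follows the injection, protocol 14.3.1), DIS (each item compares with the last visit, SAP 2.6.1) or C-SSRS (lifetime form at Day 1, since-last-visit form later, protocol 16.9). DFSS-I is also left off the list, because its recall runs back to the prior visit: nominally 28 days at Weeks 17, 30 and 43 but 91 - 28 = 63 days at Weeks 26, 39 and 52.
3. Use observed pairs only. Leave a missing pre-injection value missing in both roles, with no screening value in its place. Document this as a change from protocol 17.9, and show the site-average result as a sensitivity analysis if any value is affected.
4. As a separate short item, reconcile the neurologic-score change in protocol 17.7 with the listing in SAP 2.9.2 and 5.8.

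The data are already scheduled for collection. The cost is longer tables, a documented departure from the protocol's imputation rule, and possibly a few subjects lost from a session's paired test.
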